4 STUDY DESIGN AND RATIONALE

4.1 Overview of Study Design

This randomized, partially-blinded, active comparator-controlled multi-center, dose-finding, Phase 1/2 study will be conducted at multiple sites. The composition of QVLP to be used in this study includes a mix of recombinant H1, H3, and two B hemagglutinin proteins expressed as VLPs and will be based on the 2020-2021 recommended WHO strains for vaccination in the Northern Hemisphere. The compositions of the active comparators are also based on the 2020-2021 recommended WHO strains for vaccination in the Northern Hemisphere.

Overall, approximately 120 healthy male and female subjects 65 years of age and older will be enrolled evenly into one of three parallel treatment groups, as presented in Table 4. A dose level of 30 μ g/strain QVLP will be tested with the adjuvant AS03. The 30 μ g/strain is the full dose of QVLP, used in previous clinical studies.

Table 4 Study Treatment Groups

Treatment Group	Treatments	Dose Level	No. of Subjects
1	QVLP adjuvanted with AS03	30 μg/strain	40
2	QVLP unadjuvanted	30 μg/strain	40
3	Fluzone HD Quad	60 μg/strain	40

The first 3 subjects per treatment group enrolled in the study will receive an IM injection of one of the three treatments listed in Table 4. The vaccinations for the first three subjects in each

treatment group will be staggered so that each vaccination must be performed at least 30 minutes apart. The seven-day safety data will be collected from these subjects and reviewed by the IDMC, prior to permitting the vaccination of the remaining subjects in these three treatment groups.

Subjects will be screened up to seven days in advance of the vaccine administration and will demonstrate a satisfactory baseline medical assessment by medical history, general physical examination, urinalysis, haematological and blood biochemistry analyses, and serum screening for HIV, Hepatitis B and Hepatitis C markers. On Day 0, vaccine administration will occur. Phone contacts will be made one day and eight days after the vaccine administration, specifically for review of the subject's safety and concomitant medication data. Visits to the Investigator site will occur 3 days after the vaccine administration (Day 3) for key safety assessments and 28 days after the vaccine administration (Day 28) for key safety and immunogenicity assessments. Subjects will have monthly telephone calls after Day 28 up to the end of the study. Subjects will return to the Investigator site on Day 182 for immunogenicity and safety assessments (6-month follow-up) and on Day 365 for final immunogenicity and safety assessments (12-month follow-up).

Subjects enrolled and vaccinated in the QVLP (15 μ g/strain and 45 μ g/strain) adjuvanted with AS03 adjuvant (full dose or half dose) and the QVLP (30 μ g/strain) adjuvanted with AS03 adjuvant (half dose) treatment groups will complete study procedures as outlined above and will be followed for safety and immunogenicity assessments up to Day 365.

4.2 Rationale of Study Design

4.2.1 Randomization

Randomization will be used to minimize bias in the assignment of subjects to treatment groups, to increase the likelihood that known and unknown subject attributes (e.g. demographic and baseline characteristics) are evenly balanced across treatment groups, and to enhance the validity of statistical comparisons across treatment groups.

Subjects will be randomized according to prior influenza vaccination status defined as enrolled subjects who have received a standard influenza vaccine during the 12 months prior to study vaccination.

4.2.2 Blinding

A partially-blinded treatment trial design consisting of both observer-blind and open-label elements will be utilized in this study. Observer-blinded treatment trial design elements will be used to reduce potential bias during data collection and evaluation of the study endpoints. Details of who will remain blinded during the study are presented in Section 6.2.

Open-label trial design elements will be used to allow a small number of Medicago personnel to remain unblinded throughout the study (see Section 6.2) to make informed design decisions of

the subsequent studies based on the Day 28 and Day 182 data analyses (see Section 12.3) results, without having to wait until after the end of the follow-up period for study completion.

4.2.3 Dose Selection and Dosage Regimen

In this study, three dose levels (15 μ g/strain, 30 μ g/strain, and 45 μ g/strain) of QVLP will be tested in combination with two dose levels of AS03 adjuvant (full and half dose) in a single-dose regimen to select a dose level of QVLP and adjuvant dose level-combination that is safe and effective for further development. The 30 μ g/strain dose is the full dose of QVLP, used in previous clinical studies, and the 15 μ g/strain dose has been included to assess a possible dose-sparing effect in combination with the adjuvant AS03. A higher dose of 45 μ g/strain will also be assessed since higher doses of 45-60 μ g/strain are used by two commercially available vaccines [Flublok 2020, Fluzone High-Dose 2019] that target the elderly population.

The dosage and administration of the active comparator unadjuvanted QVLP is based on data from previous studies as dose used to establish non-inferior efficacy to another approved influenza vaccine in the elderly population. In addition, it is also the dose most comparable with commonly used licensed vaccines [Flublok 2020, Fluzone High-Dose 2019] in the elderly.

The dosage and administration of the active comparator Fluzone HD Quad is in accordance with the approved prescribing information for this vaccine.

4.2.4 Route of Administration

The route of administration used for adjuvanted QVLP and comparators is the intramuscular route, specifically in the deltoid muscle of the arm, since it is a more viable route of administration (compared to an oral route), has better absorption compared to the subcutaneous route, and is the same route of administration for the active comparators.

4.2.5 Active Comparators Selection

The active comparator unadjuvanted QVLP was selected since the safety, immunogenicity, and efficacy profile of this vaccine has been established in persons 65 years of age and older in previous studies. The same formulation of unadjuvanted QVLP will be used in combination with AS03 adjuvant.

The active comparator Fluzone HD Quad was selected on the basis that this product is an approved quadrivalent influenza vaccine for persons 65 years of age and older in the US. In addition, this product has been well-studied and has well-established immunogenicity, efficacy, and safety profiles for this population.

4.2.6 Study Duration

The duration of this study will be approximately 17 months.

5 STUDY POPULATION

5.1 Inclusion Criteria

Subjects must meet all of the following inclusion criteria at the Screening visit (Visit 1) and/or Vaccination visit (Visit 2) to be eligible for participation in this study; no protocol waivers are allowed. All Investigator assessment-based judgements must be carefully and fully documented in the source documents:

- 1. Subjects must have read, understood, and signed the informed consent form (ICF) prior to participating in the study; subjects must also complete study-related procedures and communicate with the study staff at visits and by phone during the study;
- 2. Male and female subjects must be 65 years of age and older at the Vaccination visit (Visit 2);
- 3. Subject must have a body mass index (BMI) $< 35 \text{ kg/m}^2$ at the Vaccination visit (Visit 2);
- 4. Subjects are considered by the Investigator to be reliable and likely to cooperate with the assessment procedures and be available for the duration of the study;
- 5. Subjects must be non-institutionalized (e.g. not living in rehabilitation centres or old-age homes; living in an elderly community is acceptable) and have no acute or evolving medical problems prior to study participation and no clinically relevant abnormalities that could jeopardize subject safety or interfere with study assessments, as assessed by the Principal Investigator or sub-Investigator (thereafter referred as Investigator) and determined by medical history, physical examination, serology, clinical chemistry and haematology tests, urinalysis, and vital signs. Investigator discretion will be permitted with this inclusion criterion;

Note: Subjects with a pre-existing chronic disease will be allowed to participate if the disease is stable and, according to the Investigator's judgment that must be documented in the source documents, the condition is unlikely to confound the results of the study or pose additional risk to the subject by participating in the study. Stable disease is generally defined as no new onset or exacerbation of pre-existing chronic disease three months prior to vaccination. Based on the Investigator's judgment and documented in source documentation, a subject with more recent stabilization of a disease could also be eligible.

5.2 Exclusion Criteria

Subjects who meet any of the following criteria at the Screening visit (Visit 1) and/or Vaccination visit (Visit 2) will not be eligible for participation in this study; no protocol waivers are allowed. All Investigator assessment-based judgements must be thoroughly documented in the source documents:

1. According to the Investigator's opinion, significant acute or chronic, uncontrolled medical or neuropsychiatric illness. Acute disease is defined as presence of any moderate or severe acute illness with or without a fever within 48 hours prior to the Vaccination visit (Visit 2). 'Uncontrolled' is defined as:

- Requiring a new medical or surgical treatment during the three months prior to study vaccine administration:
- Requiring any significant change in a chronic medication (i.e. drug, dose, frequency) during the three months prior to study vaccine administration due to uncontrolled symptoms or drug toxicity unless the innocuous nature of the medication change meets the criteria outlined in inclusion criterion no. 5 and is appropriately justified and documented by the Investigator.

Investigator discretion is permitted with this exclusion criterion and must be carefully and fully documented in the source documents.

- 2. Any confirmed or suspected current immunosuppressive condition or immunodeficiency, including cancer, human immunodeficiency virus, hepatitis B or C infection (subjects with a history of cured hepatitis B or C infection without any signs of immunodeficiency at present time are allowed). Investigator discretion is permitted with this exclusion criterion;
- 3. Current autoimmune disease requiring systemic treatment (such as rheumatoid arthritis, systemic lupus erythematosus, or multiple sclerosis). Investigator discretion is permitted with this exclusion criterion, and subjects may be eligible to participate with appropriate written justification in the source document (i.e. subjects with a history of autoimmune disease who are disease-free without treatment for three years or more, or on stable thyroid replacement therapy, mild psoriasis [i.e. a small number of minor plaques requiring no systemic treatment], etc.);
- 4. Administration of any non-influenza vaccine within 30 days prior to the Vaccination visit (Visit 2); planned administration of any vaccine up to Day 28 of the study. Immunization on an emergency basis during the study will be evaluated on case-by-case basis by the Investigator.
 - Note: Administration of an authorized COVID-19 vaccine prior to or during the study is acceptable;
- 5. Administration of influenza vaccine within six months prior to the Vaccination visit (Visit 2);
- 6. Administration of any adjuvanted or investigational influenza vaccine within one year prior to randomization or planned administration prior to the completion of the study;
- 7. Use of any investigational or non-registered product within 30 days or five half-lives, whichever is longer, prior to the Vaccination visit (Visit 2) or planned use during the study period. Subjects who are in a prolonged post-administration observation period of another investigational or marketed drug clinical study, for which there is no ongoing exposure to the investigational or marketed product and all scheduled on-site visits are completed, will be allowed to take part in this study, if all other eligibility criteria are met;
- 8. Administration of any medication or treatment that may alter the vaccine immune responses, such as:
 - Systemic glucocorticoids at a dose exceeding 10 mg of prednisone (or equivalent) per day for more than seven consecutive days or for 10 or more days in total, within one month prior to the Vaccination visit (Visit 2). Inhaled, nasal, intraarticular, ophthalmic, dermatological, and other topical glucocorticoids are permitted;

- Cytotoxic, antineoplastic or immunosuppressant drugs within 36 months prior to the Vaccination visit (Visit 2);
- Any immunoglobulin preparations or blood products, blood transfusion within 6 months prior to the Vaccination visit (Visit 2);
- 9. Use of any prescription antiviral drugs with the intention of COVID-19 prophylaxis, including those that are thought to be effective for prevention of COVID-19 but have not been licensed for this indication, within one month prior to the Vaccination visit (Visit 2);
- 10. Subjects at high risk of contracting SARS-CoV-2/COVID-19 infection, including, but not limited to, individuals with known close contact with:
 - anyone residing in, visiting, or working at a health care or long-term care institution (i.e. long-term care facilities, acute care hospitals, rehabilitation hospitals, mental health hospitals, emergency departments);
 - anyone with laboratory-confirmed SARS-CoV-2/COVID-19 infection within 2 weeks prior to vaccine administration;
 - anyone who traveled outside the country for any duration within 30 days before the study vaccination;
- 11. History of allergy to any of the constituents of QVLP, any components of Fluzone HD Quad, the adjuvant AS03, egg, or tobacco;
- 12. History of anaphylactic allergic reactions to plants or plants components (including fruits and nuts);
- 13. Subjects with a history of Guillain-Barré Syndrome;
- 14. Personal or family (first-degree relatives) history of narcolepsy;
- 15. Use of prophylactic medications (e.g. antihistamines [H1 receptor antagonists], nonsteroidal anti-inflammatory drugs [NSAIDs], systemic and topical glucocorticoids, non-opioid and opioid analgesics) within 24 hours prior to the Vaccination visit (Visit 2) to prevent or preempt symptoms due to vaccination;
- 16. Have a rash, dermatological condition, tattoos, muscle mass, or any other abnormalities at the injection site that may interfere with injection site reaction rating. Investigator discretion will be permitted with this exclusion criterion;
- 17. Subjects identified as an Investigator or employee of the Investigator or clinical site with direct involvement in the proposed study, or identified as an immediate family member (i.e. parent, spouse, natural or adopted child) of the Investigator or employee with direct involvement in the proposed study, or any employees of Medicago.

5.3 Prior and Concomitant Therapy

New or changed medications reported by the subject post-vaccination and through to the end of the study will be recorded in the source documents as a concomitant medication as per the conditions outlined in the next paragraph. Since AEs may be secondary to new medications, the Investigator will explore the reasons for the change or for the new medication intake and document these AEs, if any.

Concomitant medications must be reported (reason for use, dates of administration, dosage, and route) if the use meets the following conditions:

- Within 30 days preceding vaccination: any treatments and/or medications specifically contraindicated (e.g. influenza vaccines, any immunoglobulins or other blood products, or any immune modifying drugs, etc.);
- From randomization to Day 28, inclusive: any medication (including, but not limited to, over-the-counter medicines such as aspirin or antacids), vitamins, and mineral supplements;
- From Day 29 to the end of the study, inclusive: any concomitant medication(s) administered to treat a NOCD (see Section 13.1.4 for definition of NOCD), SAE, or AE leading to withdrawal; any concomitant medication used to treat an AE that occurred before Day 28 and that is still being used afterwards (i.e. on-going use);
- Any concomitant medication used to treat conditions reported as medical history;
- Any investigational medication or vaccine; any vaccine not foreseen in the study protocol.

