Oral digital thermometer and instructions on AEs ⁴		X							
Collection of solicited local/systemic AEs		X	X	X	Х				
Concomitant medications ⁵		At any time during the study period							
AEs, SAEs, AESI, MAAEs, and NOCDs ⁶		At any time during the study period							
Termination record									X

¹ Record any changes in medical history and medications and confirmation that the subject continues to meet all inclusion and no exclusion criteria since screening.

² A limited physical examination will occur at screening, Day 0, and Day 3. History/symptom-directed physical examinations may be at Day 28, Day 182, and Day 365 visits if 1) new complaints or concerns are raised by either the study subject or study staff and 2) deemed to be necessary by the Investigator.

³ Record prior to study vaccine, after the observation period and as deemed necessary.

⁴ After vaccination, subjects will be instructed on the diary and memory aid (manual or electronic) provided for their use for recording AEs and concomitant medication use.

⁵ After the Day 28 visit, concomitant medication collection will be limited to those used to treat a NOCD, SAE, AE leading to withdrawal, AESIs, MAAEs, or an AE that occurred before Day 28; any vaccine not foreseen in the study protocol; and prohibited medications.

⁶ AEs will be collected up to Day 28; SAEs, AEs leading to withdrawal, AESIs, MAAEs, and NOCDs will be collected through to the end of the study. Specific contacts for the collection of information regarding all these events will occur on Day 365 (during the Day 365 final visit) for SAEs, AEs leading to withdrawal, AESIs, MAAEs, and NOCDs.

⁷ If screening and vaccination occur on the same day (Day 0), then this test and/or procedure should only be performed once prior to randomization.

Visit Type	Screening	Vaccination	Post-vaccination Visits/Contacts						
Study Day	Day -7 to 0	Day 0	Day 1 (+ 1)	Day 3 (± 1)	Day 8 (+ 1)	Day 28 (± 2)	Monthly Calls ⁸	Day 182 (± 14) 10	Day 365
Visit Number	1	2	Phone	3	Phone	4	Phone	5	6

⁸ Subjects should be reached once a month with no more than 45 days between phone contacts (use Day 28 date as starting reference).

⁹ Sample blood collection at screening should be performed under fasting conditions (approximately 12 hours) for cholesterol and triglyceride analyses. Cholesterol and triglyceride analysis will only be performed at screening.

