10.1.9 Day 182 (Visit 5)

For some subjects, the Day 182 visit may occur during the time the subject may want to receive the 2021-2022 seasonal influenza vaccine. Hence, the tests/procedures (including immunogenicity sample collection) originally planned for the Day 182 visit will be collected at the Day 182 timepoint or immediately prior to administration of the 2021-2022 seasonal influenza vaccine (whichever comes first).

The post-vaccination visit procedures will be performed by blinded site staff members at the clinical site. For subjects in quarantine, these procedures will be performed by blinded trained medical staff at the subject's home (or place of quarantine). The following procedures will be performed during the Day 182 visit (± 14 days):

- Review the memory aid content with the subject to ensure appropriate completion.
 Corrections must be made by the subject him/herself and all corrections must be initialed and dated. Collect manual memory aid and provide subjects with another memory aid for the collection of safety data from Day 183 to Day 365;
- Review the subject's safety data and ensure all updates on concomitant medication usage and any changes in the subject's health (AEs ongoing from Day 28, SAEs, AESIs, MAAEs, or NOCDs) are recorded appropriately;
- Confirm that the subject has continued to comply with protocol requirements (e.g. no use of prohibited concomitant medications);
- Perform a vital signs measurement, including resting BP, HR, and OT;
- Collect blood samples for immunogenicity (serology) assessments and prepare and store these samples until shipment to the analytical laboratories.

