### 4.4.4. Per Protocol (PP) Sets

Four individual per protocol (PP) sets will be defined which will consist of a subset of subjects with no major protocol deviations related to subject eligibility, the ability to develop a valid immune response, prohibited medication use, or the immunogenicity analyses; and who received QVLP or the active comparators. Only protocol deviations up to the visit of interest will be observed for each PP set. In particular, immunogenicity assessments should be available on certain visits, as follows:

- Per Protocol Set 1: Day 0,
- Per Protocol Set 2: Day 0 and Day 28,

Confidential

Medicago USA Page 22 of 55

- Per Protocol Set 3: Day 0 and Day 182,
- Per Protocol Set 4: Day 0 and Day 365.

Subjects who had blood samples for immunogenicity taken outside of the time window for blood sample collection at Day 0 or the respective visit (Day 28 / Day 182 / Day 365) are to be excluded from the PP set for the specific visit. Major protocol deviations will be identified and documented by Medicago during a blinded data review prior to database lock and confirmed at the time of database lock. Assignment of subjects to each of the PP sets (yes/no) will be provided to CCI Subjects who received the wrong treatment, but for whom the treatment received can be unequivocally confirmed, will be analyzed as treated, provided they have no other deviations that compromise their data. For analyses using the Per Protocol set, subjects will be analyzed according to the vaccines actually received.

Medicago USA Page 23 of 55

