# 6.4. Prior and Concomitant Therapy

New or changed medications reported by the subject post-vaccination and through to the end of the study will be recorded in the source documents as a concomitant medication as per the conditions outlined in the next paragraph. Since AEs may be secondary to new medications, the Investigator will explore the reasons for the change or for the new medication intake and document these AEs, if any.

Concomitant medications must be reported (reason for use, dates of administration, dosage, and route) if the use meets the following conditions:

- Within 30 days preceding vaccination: any treatments and/or medications specifically contraindicated (e.g., influenza vaccines, any immunoglobulins or other blood products, or any immune modifying drugs, etc.);
- From randomization to Day 28, inclusive: any medication (including, but not limited to, over-the-counter medicines such as aspirin or antacids), vitamins, and mineral supplements;
- From Day 29 to the end of the study, inclusive: any concomitant medication(s) administered to treat a NOCD (see protocol version 4.0 Section 13.1.4 for definition of NOCD), SAE, or AE leading to withdrawal; any concomitant medication used to treat an AE that occurred before Day 28 and that is still being used afterwards (i.e., on-going use);
- Any concomitant medication used to treat conditions reported as medical history;
- Any investigational medication or vaccine; any vaccine not foreseen in the study protocol.

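### Protocol 5.3 and Table 1 footnote 5 give conflicting lists of medicines to record after Day 28, and neither clearly covers a seasonal influenza vaccine given before the Day 365 draw

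*Protocol*

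**What the plan says.** Two rules govern which medicines are recorded after Day 28, and each appears once in the Protocol and once in the SAP.

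The first is in Protocol 5.3. From Day 29 it names "any concomitant medication(s) administered to treat a NOCD (see Section 13.1.4 for definition of NOCD), SAE, or AE leading to withdrawal" and continuing treatment of AEs that began before Day 28. Two further bullets carry no time limit: "Any concomitant medication used to treat conditions reported as medical history" and investigational or unforeseen products. SAP 6.4 repeats the rule, with "SAE, or AE leading to withdrawal; any concomitant medication used to treat an AE that occurred before Day 28" and "Any investigational medication or vaccine; any vaccine not foreseen in the study protocol".

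The second is footnote 5 of Protocol Table 1, repeated as footnote 5 in SAP 13.1. It is worded as a closed list: "After the Day 28 visit, concomitant medication collection will be limited to those used to treat a NOCD, SAE, AE leading to withdrawal, AESIs", then MAAEs, AEs from before Day 28, and finally "any vaccine not foreseen in the study protocol; and prohibited medications".

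SAP 4.4.4 removes subjects with major deviations, including prohibited medication use, from the per-protocol sets, and states: "Only protocol deviations up to the visit of interest will be observed for each PP set". PP Set 3 serves Day 182 and PP Set 4 serves Day 365. Protocol 5.4 prohibits immune-altering drugs during the study. Among influenza vaccines it prohibits only adjuvanted or investigational ones.

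The protocol itself anticipates two kinds of vaccine. Section 10.1.9 has the Day 182 sample drawn at Day 182 or "immediately prior to administration of the 2021-2022 seasonal influenza vaccine (whichever comes first". Section 5.2 accepts authorized COVID-19 vaccines before or during the study.

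**The concern.** A site cannot follow both rules, because footnote 5 is exclusive and the lists differ. The difference matters because the per-protocol set is the primary analysis set for immunogenicity, and PP Sets 3 and 4 depend on knowing about prohibited drugs taken up to Day 182 and Day 365. Protocol 5.3 has no item for prohibited drugs as such.

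The vaccine wording leaves a gap under either rule. A second influenza vaccine before the Day 365 draw can raise the HI titer that is meant to show how long the response to the study vaccine lasts. If product and date are not recorded, those subjects cannot be identified or examined separately. The dates of any vaccine, including COVID-19 vaccines, also bear on how AEs after Day 28 are interpreted.

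**Working it through.** The plan states no figure to reproduce here; SAP 4.1 says no sample-size calculation was made. The check is a comparison of the texts, followed by an illustration of scale.

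**Step 1. The two lists side by side, after Day 28.**

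| Item | Protocol 5.3 / SAP 6.4 | Footnote 5, Protocol Table 1 / SAP 13.1 |
|---|---|---|
| Treatment of NOCD, SAE, AE leading to withdrawal | yes | yes |
| Treatment of an AE from before Day 28 | yes, if ongoing | yes |
| Treatment of AESI | no | yes |
| Treatment of MAAE | no | yes |
| Prohibited medications | no such item | yes |
| Treatment of medical-history conditions | yes | no |
| Investigational products | yes, by name | covered as prohibited |
| Unforeseen vaccines | yes | yes |
| 2021-2022 seasonal influenza vaccine | not clearly | not clearly |
| Authorized COVID-19 vaccine | not clearly | not clearly |

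Three classes appear only in footnote 5 (AESI treatment, MAAE treatment, prohibited medications). One substantive class appears only in 5.3 (medical-history treatment).

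**Step 2. An example.** Take a systemic glucocorticoid course above the Section 5.4 limit, given after Day 28 for a new medically attended illness that is not serious, not chronic and does not lead to withdrawal. Under 5.3 no item applies, so it is not reportable. Under footnote 5 it is reportable twice, as MAAE treatment and as a prohibited medication. SAP 4.4.4 needs this record to decide membership of PP Set 3 or 4.

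**Step 3. Vaccines.** Both rules reach only vaccines the protocol does not foresee. Sections 10.1.9 and 5.2 foresee the two products above, and Section 5.4 prohibits neither, so the prohibited-medication item does not catch them.

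**Step 4. Timing.** SAP 1 dates Protocol 4.0 to 8 March 2021. A subject vaccinated that day reaches Day 182 on 6 September 2021 (window of 14 days either side: 23 August to 20 September) and Day 365 on 8 March 2022. With vaccination on 30 April 2021 (an assumed date), Day 182 is 29 October 2021 and Day 365 is 30 April 2022. Much or all of autumn 2021 therefore lies before the Day 365 draw. The draw-before-vaccination rule applies to Day 182; Day 365 has no counterpart.

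**Step 5. Scale, on assumed inputs.** Let a share *f* of a group receive a seasonal vaccine that multiplies their Day 365 titers by *k*. The mean log titer rises by *f* × log *k*, so the group GMT is multiplied by *k*^*f*.

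| *f* | *k* = 1.5 | *k* = 2 | *k* = 4 |
|---|---|---|---|
| 25% | 1.11 | 1.19 | 1.41 |
| 50% | 1.22 | 1.41 | 2.00 |
| 75% | 1.36 | 1.68 | 2.83 |

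The Day 365/Day 0 GMFR is multiplied by the same factor, since Day 0 is unaffected. If *f* and *k* were equal in all groups, the factor would cancel in the ratio of two groups' GMTs, but it would stay in each group's own GMT and GMFR. The documents give neither *f* nor *k*.

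**The case against.** A reader might infer that PP Sets 3 and 4 cannot be built as defined. The documents do not support that. Footnote 5 collects prohibited medications to the end of the study. SAP 5.1 has all deviations reviewed before database lock. Protocol 17.1 requires departures from the protocol to be reflected in the eCRF and source documents. The monthly calls (10.1.8) ask about all medication, and Visits 5 and 6 (10.1.9, 10.1.10) review medication updates and check for prohibited use. The sets can be built if these provisions are followed.

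The residual gap in 5.3 is also narrow: drugs for SAEs, NOCDs and medical-history conditions are still captured, and Section 5.4 says only that inclusion in an analysis set may be affected. The documents offer no rate from which to count subjects wrongly kept.

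Nor does an unrecorded seasonal or COVID-19 vaccine put anyone wrongly into a per-protocol set, since neither is a stated exclusion. Day 182 is largely protected by the early draw. Visit dates are required source data, so an early draw shows from its own date, and one outside the window removes the subject from PP Set 3. A site might also read the vaccine wording as covering anything other than study treatment.

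What stands is that the safeguards are partial. The calls record medication in source documents, while SAP 7 works from the eCRF. The memory aid (17.3.1) asks only for reportable medication, so it inherits the conflict. The Visit 5 and 6 compliance check is directed at prohibited products and would not bring out a standard seasonal vaccine. SAP 8.2 has no rule for a Day 365 titer that follows one, and the ITT sensitivity analysis would not remove the effect.

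**Conclusion.** The conflict is plain in both documents and should be reconciled. Its consequence is incomplete or uneven capture of the deviations behind PP Sets 3 and 4 where a site works from 5.3. The vaccine gap rests on a literal but natural reading of the wording. Its main effect is at Day 365, where an influenza vaccine could raise titers in subjects who cannot then be identified. The 1.11- to 2.83-fold range shows what would follow from the assumed uptake and rise; it is not an estimate for this trial.

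The scope is limited to the secondary durability endpoints, mainly Day 365, and the interpretation of late AEs. The primary Day 28 analysis is unaffected, because all medication is recorded to Day 28. A reader might also infer that COVID-19 vaccines distort influenza HI titers. Nothing in the documents says so; their dates matter here for late AEs.

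**What to change.** Reconcile Protocol 5.3, Protocol Table 1 footnote 5, SAP 6.4 and SAP 13.1 footnote 5 into one list for use after Day 28. It should include treatments for AESIs and MAAEs and every medication named in Section 5.4, and should settle whether medical-history treatment is recorded.

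In the same four places, replace the restriction to unforeseen vaccines with a requirement to record the product and date of any vaccine through Day 365, naming seasonal influenza and COVID-19 vaccines. Ask for this at the existing monthly calls and at Visits 5 and 6. For contacts already made, the call notes in the source documents are the place to look.

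Add to SAP 8.2 how Day 365 HI titers after a seasonal influenza vaccine are handled, for example by a sensitivity analysis that excludes them. Recording the dates without such a rule would leave the Day 365 analysis unchanged.

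The cost is wording in four places, one statement in the SAP, a few more eCRF lines per subject and one extra analysis. No visit is added and no rule on treatment changes.
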